5.0 Safety Tabulation and Analysis

5.1 Occurrence of adverse events and adverse drug reactions / infections

5.1.1 Occurrence of adverse events

(1) Patients to be tabulated and analyzed

Safety Analysis Set

(2) Details of tabulation and analysis

The following will be tabulated for adverse events.

Total patients and patients who are taking concomitant insulin preparation, rapid-acting insulin secretagogues, SGLT-2 inhibitors, or other drugs will be tabulated.

Parameter	Details of analysis
Number of patients with adverse events	Number of patients who experienced adverse events.
Number of adverse events	Number of adverse events. Count as an event if the same adverse event (LLT) occur multiple times in a patient. Count as different events for different LLTs even if they have the same PT.
Percent of patients with adverse events	Described in Section 1.1.
Type of adverse events	Will be broadly divided into the SOCs and tabulated by PT in the SOCs. In case of the laboratory test-related events, type of adverse events will be broadly divided into the SOCs and HLGTs for tabulation by PT. For the SOCs, the number of patients with adverse events and percent of patients with events will be described in the order of SOCs agreed internationally. For the PTs, the number of adverse events and percent of events will be described in the ascending order of PT codes. Count as an event if the same adverse event (LLT) occur multiple times in a patient. Count as different events for different LLTs even if they have the same PT.

(3) Number of tables and figures

Table 5.1.1-1

5.1.2 Occurrence of adverse drug reactions / infections

(1) Patients to be tabulated and analyzed

Safety Analysis Set

(2) Details of tabulation and analysis

The following will be tabulated for adverse drug reactions, etc. and serious adverse drug reactions, etc.

Total patients and patients who are taking concomitant insulin preparation, rapid-acting insulin secretagogues, SGLT-2 inhibitors, or other drugs will be tabulated.

Parameter	Details of tabulation and analysis
Number of patients with adverse drug reactions, etc.	Number of patients who experienced adverse drug reactions, etc.
Number of adverse drug reactions, etc.	Number of adverse drug reactions, etc. Count as an event if the same adverse drug reactions, etc. (LLT) occur multiple times in a patient. Count as different events for different LLTs even though they have the same PT.
Percent of patients with adverse drug reactions, etc.	Described in Section 1.1.
Type of adverse drug reactions, etc.	Will be broadly divided into the SOCs and tabulated by PT in the SOCs. In case of the laboratory test-related events, type of adverse events will be broadly divided into the SOCs and HLGTs for tabulation by PT. For the SOCs, the number of patients with adverse drug reactions, etc. and percent of patients with adverse drug reactions, etc. will be described in the order of SOCs agreed internationally. For the PTs, the number of adverse drug reactions, etc. and percent of adverse drug reactions, etc. will be described in the ascending order of PT codes. Count as an event if the same adverse drug reactions, etc. (LLT) occur multiple times in a patient. Count as different events for different LLTs even though they have the same PT.

(3) Number of tables and figures

Tables 5.1.2-1 and 5.1.2-2

5.1.3 Important Identified Risks, Important Potential Risks, and Important Missing Information

(1) Patients to be tabulated and analyzed

Safety Analysis Set

(2) Details of tabulation and analysis

The following will be tabulated for important identified risks, important potential risks, and important missing information (described in Section 1.2).

Total patients and patients who are taking concomitant insulin preparation, rapid-acting insulin secretagogues, SGLT-2 inhibitors, or other drugs will be tabulated.

Parameter	Details of tabulation and analysis
-----------	------------------------------------

Parameter	Details of tabulation and analysis
Number of patients with adverse events (or adverse drug reactions, etc.)	Number of patients who experienced adverse events (or adverse drug reactions, etc.) with important identified risks, important potential risks, and important missing information.
Number of adverse events (or adverse drug reactions, etc.)	Number of adverse events (or adverse drug reactions, etc.) with important identified risks, important potential risks, and important missing information. Count as an event if the same adverse event (or adverse drug reaction, etc.) (LLT) occur multiple times in a patient. Count as different events for different LLTs even if they have the same PT.
Percent of patients with adverse events (or adverse drug reactions, etc.)	Described in Section 1.1.
Type of adverse events (or adverse drug reactions, etc.)	Will be broadly divided into the important identified risks, important potential risks, and important missing information and tabulated by PT in them. For the PTs, the number of adverse events (or adverse drug reactions, etc.) and percent of adverse events (or adverse drug reactions, etc.) will be described in the ascending order of PT codes. Count as an event if the same adverse event (or adverse drug reaction, etc.) (LLT) occur multiple times in a patient. Count as different events for different LLTs even though they have the same PT.

(3) Number of tables and figures

Tables 5.1.3-1 and 5.1.3-2

5.2 Occurrence of Adverse Events and Adverse Drug Reactions / Infections in the Not Safety Analysis

Set

5.2.1 Occurrence of Adverse Events

(1) Patients to be tabulated and analyzed

Not Safety Analysis Set

(2) Details of tabulation and analysis

The following will be tabulated.

Total patients and patients who are taking concomitant insulin preparation, rapid-acting insulin secretagogues, SGLT-2 inhibitors, or other drugs will be tabulated.

Parameter	Details of tabulation and analysis
Number of patients with adverse events	Number of patients who experienced adverse events.
Number of adverse events	Number of adverse events. Count as an event if the same adverse event (LLT) occur multiple times in a patient. Count as different events for different LLTs even if they have the same PT.
Percent of patients with adverse events	Described in Section 1.1.
Type of adverse events	Will be broadly divided into the SOCs and tabulated by PT in the SOCs. In case of the laboratory test-related events, type of adverse events will be broadly divided into the SOCs and HLGTS for tabulation by PT. For the SOCs, the number of patients with adverse events and percent of patients with events will be described in the order of SOCs agreed internationally. For the PTs, the number of adverse events and percent of events will be described in the ascending order of PT codes. Count as an event if the same adverse event (LLT) occur multiple times in a patient. Count as different events for different LLTs even though they have the same PT.

(3) Number of tables and figures

Table 5.2-1

5.2.2 Occurrence of adverse drug reactions / infections

(1) Patients to be tabulated and analyzed

Not Safety Analysis Set

(2) Details of tabulation and analysis

The following will be tabulated.

Total patients and patients who are taking concomitant insulin preparation, rapid-acting insulin secretagogues, SGLT-2 inhibitors, or other drugs will be tabulated.

Parameter	Details of tabulation and analysis
Number of patients with adverse drug reactions, etc.	Number of patients who experienced adverse drug reactions, etc.
Number of adverse drug reactions, etc.	Number of adverse drug reactions, etc. Count as an event if the same adverse drug reactions, etc. (LLT) occur multiple times in a patient. Count as different events for different LLTs even if they have the

	same PT.
Percent of patients with adverse drug reactions, etc.	Described in Section 1.1.
Type of adverse drug reactions, etc.	
Will be broadly divided into the SOCs and tabulated by PT in the SOCs. In case of the laboratory test-related events, type of adverse events will be broadly divided into the SOCs and HLGTS for tabulation by PT.
 
For the SOCs, the number of patients with adverse drug reactions, etc. and percent of patients with adverse drug reactions, etc. will be described in the order of SOCs agreed internationally.
 
For the PTs, the number of adverse drug reactions, etc. and percent of adverse drug reactions, etc. will be described in the ascending order of PT codes. Count as an event if the same adverse drug reactions, etc. (LLT) occur multiple times in a patient. Count as different events for different LLTs even though they have the same PT.

(3) Number of tables and figures

Table 5.2-2

5.3 Occurrence of Adverse Drug Reactions / Infections by Severity, Onset Period, and Outcome

5.3.1 Occurrence of Adverse Drug Reactions / Infections by Severity, Onset Period, and Outcome

(1) Patients to be tabulated and analyzed

Safety Analysis Set

(2) Details of tabulation and analysis

Each parameter will be categorized by the categories described below to tabulate the type of adverse drug reactions, etc.

Total patients and patients who are taking concomitant insulin preparation, rapid-acting insulin secretagogues, SGLT-2 inhibitors, or other drugs will be tabulated.

Parameter	Category
Severity	Serious, Not serious, Not described
Onset period	1 to 14 days, 15 to 28 days, 29 to 84 days, 85 to 168 days, 169 to 336 days, 337days or Unknown
Outcome	Resolved, Resolving, Not resolved, Resolved with sequelae, Death, or Unknown

The method for tabulation of type adverse drug reactions, etc. is described below:

Parameter	Details of tabulation and analysis
Type of adverse drug	Will be broadly divided into the SOCs and tabulated by PT in the

Parameter	Details of tabulation and analysis
reactions, etc.	
SOCs. In case of the laboratory test-related events, type of adverse events will be broadly divided into the SOC and HLGs for tabulation by PT.
 
For the SOC, the number of patients with adverse drug reactions, etc. will be described in the order of SOC agreed internationally.
 
For the PTs, the number of adverse drug reactions, etc. will be described in the ascending order of PT codes. Count as an event if the same adverse drug reactions, etc. (LLT) occur multiple times in a patient. Count as different events for different LLTs even if they have the same PT. However, evaluate an event for the same LLT in accordance with the following order of priority:
 
Onset period: earlier event
 
Severity: Serious → Not serious → Not described
 
Outcome: Death → Resolved with Sequelae → Not resolved → Resolving → Resolved → Unknown

(3) Number of tables and figures

Tables 5.3-1 to 5.3-3

5.4 Patient Demographics and Frequency of Adverse Drug Reactions / Infections by Treatment

5.4.1 Patients demographics and Frequency of Adverse Drug Reactions / Infections by Treatment

(1) Patients to be tabulated and analyzed

Safety Analysis Set

(2) Details of tabulation and analysis

Each parameter will be categorized by the categories described below to tabulate the percent of patients with adverse drug reactions, etc.

The Fischer exact test will be used for parameters without rank data. The Mann-Whitney U test will be used for parameters with rank data. (The tests will be used for parameters with asterisk [*].)

Total patients and patients who are taking concomitant insulin preparation, rapid-acting insulin secretagogues, SGLT-2 inhibitors, or other drugs will be tabulated.

Parameter	Category
Sex*	Male, Female
Age*	< 65 years, ≥ 65 years
	< 75 years, ≥ 75 years
Concurrent liver disorder*	No, Yes
Severity of hepatic	Normal, Grades 1, 2, and 3, or Unknown

Parameter	Category
impairment*	
Concurrent renal disorder*	No, Yes
Severity of renal impairment* (eGFR)	Normal + Mild, Moderate + Severe, or Unknown
Severity of renal impairment* (serum creatinine)	Normal + Mild, Moderate + Severe, or Unknown
Concurrent heart disease*	No, Yes
Details of concurrent heart disease (overlapped)	Cardiac failure, myocardial infarction, or angina pectoris
Concurrent cardiac failure*	No, Yes
Severity classification of cardiac failure (NYHA classification)*	Classes NYHA I, NYHA II, NYHA III, and NYHA IV, or Unknown
Concurrent stroke-related disease*	No, Yes, or Unknown
Mean daily dose of Nesina	> 25 mg, 25 to >12.5 mg, 12.5 to > 6.25 mg, or ≤ 6.25 mg
Administration of concomitant medication (diabetic drug)	No, Yes
Concomitant medications (diabetic drugs) (overlapped)	α-glucosidase inhibitors, thiazolidines, sulfonylureas, biguanides, rapid-acting insulin secretagogues, or insulin preparations, DPP-4 inhibitors, GLP-1 receptor agonists, SGLT-2 inhibitors, combination of diabetic drugs, or other diabetic drugs
Administration of concomitant medication (protease drug)*	No, Yes, or Unknown
Administration of	No, Yes, or Unknown

Parameter	Category
concomitant medication (combined with renal excretory drug)*	

(3) Number of tables and figures

Table 5.4.1-1

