#### 10.4.2 Factors Probably Affecting Safety

For adverse drug reactions reported in the observation period, the frequency of patient demographics (e.g., sex, age), details of treatment (e.g., status of Nesina, and status of concomitant medications) will be stratified.

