Severity of hepatic impairment	
Severity of hepatic impairment will be assessed using AST or ALT at the start of Nesina treatment. Severity will be assessed using the categories described below, and the higher grade of AST or ALT will be used for analysis.
 
Normal: < 50 IU/L
 
Grade 1: ≥ 50 IU/L and < 100 IU/L
 
Grade 2: ≥ 100 IU/L and < 500 IU/L
 
Grade 3: ≥ 500 IU/L
 
Quoted from the Standards for Classification of Serious Adverse Drug Reactions due to Drug Products notified by the director of Pharmaceuticals and Chemicals Safety Division, Pharmaceutical Affairs Bureau, the Ministry of Health and Welfare (No. 80 notification of Pharmaceuticals and Chemicals Safety Division, Pharmaceutical Affairs Bureau: June 29, 1992).

Severity of renal impairment (eGFR)	
eGFR* will be calculated based on age and serum creatinine at the start of Nesina treatment to assess the severity according to the categories described below. For unknown serum creatinine and age at the start of Nesina treatment, indicate as unknown. Indicate to one decimal place rounded from two decimals.
 
Normal: ≥ 90 mL/min/1.73 m²
 
Mild: ≥ 60 mL/min/1.73 m² and < 90 mL/min/1.73 m²
 
Moderate: ≥ 30 mL/min/1.73 m² and < 60 mL/min/1.73 m²
 
Severe: < 30 mL/min/1.73 m²
 
*eGFR = 194 × Cr^{-1.094} × age (year)^{-0.287} (×0.739 for females)

Term	Definition
	Cr: Serum creatinine at the start of Nesina treatment. For serum Cr, indicate to two decimal places. Quoted from the Clinical Practice Guide for CKD, edited by the Japanese Society of Nephrology.
Severity of renal impairment (serum creatinine)	Severity will be assessed based on serum creatinine at the start of Nesina treatment and according to the following categories: Normal + Mild: Males: ≤ 1.4 mg/dL, Females: ≤ 1.2 mg/dL Moderate: Males: > 1.4 mg/dL to ≤ 2.4 mg/dL, Females: > 1.2 mg/dL to ≤ 2.0 mg/dL Severe: Males: > 2.4 mg/dL, Females: > 2.0 mg/dL For undescribed serum creatinine level at the start of Nesina treatment, indicate as unknown.

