1.4 Level of Significance and Confidence Coefficient

Two-sided 5%, two-sided 95%.

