5.4 Patient Demographics and Frequency of Adverse Drug Reactions / Infections by Treatment

5.4.1 Patients demographics and Frequency of Adverse Drug Reactions / Infections by Treatment

(1) Patients to be tabulated and analyzed

Safety Analysis Set

(2) Details of tabulation and analysis

Each parameter will be categorized by the categories described below to tabulate the percent of patients with adverse drug reactions, etc.

The Fischer exact test will be used for parameters without rank data. The Mann-Whitney U test will be used for parameters with rank data. (The tests will be used for parameters with asterisk [*].)

Total patients and patients who are taking concomitant insulin preparation, rapid-acting insulin secretagogues, SGLT-2 inhibitors, or other drugs will be tabulated.

Parameter	Category
Sex*	Male, Female
Age*	< 65 years, ≥ 65 years
	< 75 years, ≥ 75 years
Concurrent liver disorder*	No, Yes
Severity of hepatic	Normal, Grades 1, 2, and 3, or Unknown

Parameter	Category
impairment*	
Concurrent renal disorder*	No, Yes
Severity of renal impairment* (eGFR)	Normal + Mild, Moderate + Severe, or Unknown
Severity of renal impairment* (serum creatinine)	Normal + Mild, Moderate + Severe, or Unknown
Concurrent heart disease*	No, Yes
Details of concurrent heart disease (overlapped)	Cardiac failure, myocardial infarction, or angina pectoris
Concurrent cardiac failure*	No, Yes
Severity classification of cardiac failure (NYHA classification)*	Classes NYHA I, NYHA II, NYHA III, and NYHA IV, or Unknown
Concurrent stroke-related disease*	No, Yes, or Unknown
Mean daily dose of Nesina	> 25 mg, 25 to >12.5 mg, 12.5 to > 6.25 mg, or ≤ 6.25 mg
Administration of concomitant medication (diabetic drug)	No, Yes
Concomitant medications (diabetic drugs) (overlapped)	α-glucosidase inhibitors, thiazolidines, sulfonylureas, biguanides, rapid-acting insulin secretagogues, or insulin preparations, DPP-4 inhibitors, GLP-1 receptor agonists, SGLT-2 inhibitors, combination of diabetic drugs, or other diabetic drugs
Administration of concomitant medication (protease drug)*	No, Yes, or Unknown
Administration of	No, Yes, or Unknown

Parameter	Category
concomitant medication (combined with renal excretory drug)*	

(3) Number of tables and figures

Table 5.4.1-1

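### The one-factor-at-a-time tests in SAP 5.4.1 cannot separate age from renal function, so an age effect on ADRs can appear as a renal association

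*SAP*

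**What the plan says.** Protocol 10.4.2, whose heading concerns factors that may affect safety, plans a stratified presentation: "For adverse drug reactions reported in the observation period, the frequency of patient demographics (e.g., sex, age), details of treatment" and so on are to be stratified. Protocol 10.6 singles out elderly patients and patients with hepatic or renal impairment for separate description.

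SAP 5.4.1 carries this out with a table of the percentage of patients with ADRs by category, plus tests on the asterisked parameters: "The Fischer exact test will be used for parameters without rank data. The Mann-Whitney U test will be used for parameters with rank data". SAP 1.4 sets the level ("Two-sided 5%, two-sided 95" percent). Counting asterisks gives 14 tests per population: sex, age at 65, age at 75, liver disorder, hepatic severity, renal disorder, eGFR class, creatinine class, heart disease, cardiac failure, NYHA class, stroke-related disease, protease drug and renal excretory drug.

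Three of these describe the kidney. For the first, SAP 1.1 says "eGFR* will be calculated based on age and serum creatinine at the start of Nesina treatment", with the class boundary at 60 ("Moderate: ≥ 30 mL/min/1.73 m² and < 60 mL/min/1.73 m²"). For the second, "Severity will be assessed based on serum creatinine at the start of Nesina treatment and according to the following categories", with cut-offs by sex and no age term. The third is concurrent renal disorder, a coded yes/no. Both severity factors enter 5.4.1 as "Normal + Mild, Moderate + Severe, or Unknown".

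SAP 5.5 to 5.18 then tabulate ADR types by one factor at a time. The only further breakdown is by concomitant-drug group. Neither document contains a regression, an age-by-renal cross-table or any other adjustment.

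**The concern.** Age and renal function are two of the characteristics that the protocol most wants described, and the plan gives no means of telling them apart. eGFR class is partly age by construction. In any population where creatinine also rises with age, the two are linked more closely still. If older patients have more ADRs for reasons unrelated to the kidney, the eGFR below 60 row will tend to show more ADRs too, and its p-value will look like evidence about renal function. The reverse can also happen, with a real renal effect showing in the age rows.

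Splitting by treatment group does not help, because age and renal function stay linked within each group. At stake is the explanation given for an ADR difference: a renal caution might be drawn from what is an age effect, or the other way round.

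**Working it through.** **Inputs from the documents.** Two-sided 5% (SAP 1.4). The eGFR formula and the split at 60 (SAP 1.1, 5.4.1). N = 1,000, and past-survey shares of 58.0% elderly and 15.1% with renal impairment (Protocol 3.2, which does not say how renal impairment was defined).

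**Assumptions, not in the documents.** The ADR rate, the age effect on ADRs, the age and creatinine distributions, any rise of creatinine with age, and no patients in the Unknown class.

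**Step 1: does the 5% level hold?** It is a setting, so the check is the size of the tests when ADRs do not depend on age (N = 1,000, 15.1% with eGFR below 60, 5% ADRs, 5,000 runs). Fisher rejects in 3.9–4.3% and Mann-Whitney in 4.7–5.1%. The level holds.

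**Step 2: how strong is the formula link?** eGFR = 194 × Cr^-1.094 × age^-0.287 (× 0.739 for females). For a man with creatinine 0.95 mg/dL, 0.95^-1.094 = 1.0577.
- Age 50: 194 × 1.0577 × 0.3254 = 66.8, Normal + Mild.
- Age 80: 194 × 1.0577 × 0.2843 = 58.3, Moderate + Severe.

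The same creatinine changes class through age alone. The link is modest, though: from 55 to 75 the age term multiplies eGFR by (75/55)^-0.287 = 0.915, a fall of 8.5%. If log-creatinine also rises 0.008 per year, 20 years multiply creatinine by exp(0.16) = 1.174, and eGFR by 1.174^-1.094 × 0.915 = 0.768.

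**Step 3: how often is the renal row significant when only age matters?** Settings: N = 1,000; age mean 67.2, SD 11; 60% male; log-creatinine SD 0.25; 25–29% with eGFR below 60; ADR rate 5% or 10%; age odds ratio 1.5 or 1.8 per 10 years; no renal effect; 1,200 surveys per setting.

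| Rise of creatinine per year | Fisher, eGFR <60 vs ≥60 |
|---|---|
| none (formula link only) | 5.3–11.2% |
| 0.5% | 12.8–37.1% |
| 0.8% | 16.7–54.6% |

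A likelihood-ratio test adjusted for age and sex rejects in 4.5–6.6% across all settings. The simulation error near 5% is √(0.05 × 0.95/1,200) = 0.6 percentage points, so the 5.3% at the bottom of the first row cannot be told from 5%. A second simulation gave about 5–9% for the formula link alone, about 10–50% with a creatinine rise, and about 3–7% after adjustment.

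**Step 4: sensitivity using the protocol's 15.1%.** Age SD 12, log-creatinine SD 0.25, 5% ADRs, 5,000 runs. Cells are Fisher / Mann-Whitney.

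| Age effect on ADRs | Formula link only | Plus age–creatinine correlation 0.3 |
|---|---|---|
| OR 2, ≥65 vs <65 | 5.1% / 6.4% | 7.0% / 8.9% |
| OR 3, ≥65 vs <65 | 6.0% / 7.4% | 10.9% / 13.0% |
| OR 2 per 10 years | 9.9% / 12.0% | 38.9% / 43.7% |

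Logistic regression with age gives 4.5–5.4% in these six cells. In a treatment group of 300 (assumed size) with OR 2 for ≥65, Fisher stays at 3.9–4.5%, so the Total column is where this matters.

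**The case against.** The protocol asks for stratified frequencies, not for causal effects. It says that the sample size has no statistical basis, and no rule in the SAP turns a p-value into a statement about cause. One-factor tables are a faithful execution of that request. This stands, and it limits the point to an improvement: nothing planned is invalid. But the SAP attaches p-values at a stated level without calling them exploratory, under a protocol heading about factors affecting safety, so readers will use them for attribution.

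A renal factor with no age in its definition, creatinine class, is also tested. That removes the formula link for that row but does nothing about creatinine rising with age.

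Stronger readings are tempting and should be resisted:
- *The tests run well above their 5% level.* They do not. Step 1 shows that the level holds for the hypothesis each test examines, a crude difference in ADR frequency. The excess in Steps 3 and 4 is detection of a real but confounded crude difference. Its larger values need a steep age effect or an age trend in creatinine, and the documents give neither.
- *The survey would name the wrong patients.* In the scenarios here, patients with eGFR below 60 really do have more ADRs, because they are older. Only the explanation would be wrong.
- *The heart, stroke and co-medication rows suffer equally.* Those factors may well be linked to age, but the documents give nothing from which to size it, and it was not computed.

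**Conclusion.** The point holds as a matter of attribution. The current SAP 5.4.1 has no analysis that separates age from renal function, while SAP 1.1 builds age into eGFR, so an age effect on ADRs can appear as a renal association.

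With N = 1,000, ADR rates of 5–10%, an age odds ratio of 1.5–1.8 per 10 years and no renal effect, the eGFR below 60 row is significant in about 5–11% of surveys through the formula alone. With creatinine also rising 0.5–0.8% per year, the figure is about 10–55%. Apart from N, these inputs are assumptions, so the ranges show what could happen and do not predict this survey. Creatinine class and concurrent renal disorder were not simulated; they belong to the point because they describe the same organ and are equally unadjusted. The change is worth making because it is cheap and goes to the question that the table is meant to inform.

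**What to change.** For the Total column of SAP 5.4.1, fit one logistic regression of ADR yes/no for each renal factor (eGFR class, creatinine class, concurrent renal disorder), with age in years and sex as the other covariates. Use the Firth penalty if ADRs are few. Report the adjusted odds ratio and 95% CI beside the existing univariate p-value, and label the univariate p-values exploratory and unadjusted.

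Keep the unadjusted rows. They describe who has more ADRs, and an adjusted estimate should not be the only ground for describing a factor as relevant: with a renal term in the model, the age coefficient no longer gives the overall association of age with ADRs. Treatment group need not be in the model. SAP 1.1 defines the three drug groups as mutually exclusive, so a patient on two of the three classes fits none of them and would be lost.

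The cost is three small models and one added table block, from variables the SAP already derives. The drawbacks are that patients with unknown eGFR or creatinine drop out of the relevant model, and that intervals will be wide if ADRs are few. The adjustment checked above was ordinary logistic regression with age, or age and sex; the Firth version was not simulated.
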